** Video Nystagmography: Six standardized VNG tests (3 static: Horizontal fixation, Vertical fixation, Spontaneous nystagmus; and 3 dynamic: Random saccades, Smooth pursuit, Optokinetic) will be used to test and score subject eye fixation stability and movement control. VisualEyes™ is the standard for video nystagmographic observation, recording, and playback of ocular movements. Because the visual system is a primary contributor to motor, social, cognitive, and emotive functions, and oculomotor deficits require a significant, if unconscious, amount of attention in persons with TBI. Consequently, oculomotor monitoring methods that can observe this demand on the injured brain can be used to quantify any effects of neurorehabilitation due to the CN-NINM intervention.

Data Safety and Monitoring Plan

All study records will be structured and maintained as required under 21 CFR 812.140, and the investigators will make reports as required under 21 CFR 812.150.

Unanticipated adverse device effects

1. The PI and the Medical Advisor will immediately conduct an evaluation of any unanticipated adverse device effect.

2. If the investigators determine that an unanticipated adverse device effect presents an unreasonable risk to subjects, they shall terminate all investigations or parts of investigations presenting that risk as soon as possible. Termination shall occur no later than 5 working days after the investigators make this determination and no later than 10 working days after the investigators first received notice of the effect.
3. If the investigation was terminated due to unanticipated adverse device effects, the investigation may not resume without IRB approval.

Missing Data

We do not plan to recruit additional subjects to replace dropouts because we have increased the sample size to account for potential dropouts. We will make efforts to obtain follow-up data on subjects who withdraw from treatment. Due to the pilot nature of the study, we do not plan to do imputation for missing data points. Instead we will do a complete case analysis as well as a sensitivity analysis to examine the effect of the missing outcome data.

Compliance

We will respect the principle of Intention to Treat and will not remove subjects for protocol non-compliance. We have established the following *a priori* definition of compliance:

Subjects who miss more than 20% during any one-week period will be considered noncompliant with the training protocol.

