The primary outcome measure is the Composite SOT score. Observational measures are the Neurobehavioral Symptom Inventory, California Verbal Learning Test, Brief Symptom Inventory, Wechsler Adult Intelligence Scale – Symbol Search and Coding, Pittsburgh Sleep Quality Index, Headache Disability Index, Physiologic Stress Response, Quantitative Gait Assessment using EMG, 6 minute walk test, Dynamic Gait Index, and Computerized Video Nystagmography. The observational measures will provide essential data for potential future studies investigating CN-NINM effects on a particular functional deficit.

Data Analysis

An interim analysis will be performed when 22 subjects have completed the second phase (At-Home Training), and a full investigation at the completion of the study.

- **Interim Analysis:** In compliance with the request from the funding agency (US Army Medical Research and Materiel Command), a single independent interim analysis will be conducted under a Statistical Analysis Plan (SAP) developed for this study and reviewed by the Biostatistics Group at ICTR. The primary independent measure: Active vs. Control PoNS. The interim analysis will be performed after 22 subjects have completed the 6th data point (at 14 weeks - the completion of the At-Home phase of the study)

The primary analysis will be conducted under the intention-to-treat principal, and all data will be included. We will not conduct a missing data imputation analysis. Every attempt will be made to obtain follow-up data on subjects who withdraw from treatment.

The interim analysis will be performed using the primary efficacy endpoint for the data of first 22 subjects that have completed the Week 2 and Week 14 visits. The two treatment groups will be listed only as "Group 1" and "Group 2" to maintain the blinding of the treatments.

The number of subjects (most likely 11), and both the Mean and standard deviation (SD) for each group will be calculated by the study statistician. Student's *t*-test will be used to compare the two means. A *p*-value will be generated but no decision will be made at the interim analysis time, and the trial will continue to completion unless there are serious safety concerns.

The study statistician will present the interim analysis results (*n*, Mean, and SD) by treatment group in unblinded fashion including the *p*-value to the DSMC.

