3.0 STATISTICAL CONSIDERATIONS

3.1 Sample Size Calculations

This study is an investigation to discover changes in the Composite SOT scores of subjects from baseline at the end of Week 2 and Week 14 visits in Active and Control groups.

The sample size for the study is based on the primary endpoint of change in mean SOT score from baseline at the end of Week 2 and Week 14 visits. The following assumptions are made:

- Control group response is half of that of the Active group
- Two-sided Test
- Equal variances in both groups
- Alpha Level= 0.05
- Power = 80%
- μ_{A1} = Mean change in SOT score from baseline to the end of Week 2 visit in Active group
- μ_{A2} = Mean change in SOT score from baseline to the end of Week 14 visit in Active group.
- μ_{C1} = Mean change in SOT score from baseline to the end of Week 2 visit in Control group
- μ_{C2} = Mean change in SOT score from baseline to the end of Week 14 visit in Control group.

To calculate the sample size, the following two hypotheses, Null (H_0) and Alternative (H_A) are formulated:

$$H_0: \mu_A = 2\mu_C \quad \text{VS.} \quad H_A: \mu_A \neq 2\mu_C$$

Since there is very limited experience on PoNS™ device and no data on control device, to calculate a sample size for this study, the mean change of 26.3 in composite SOT score at the end of Week 2 visit from baseline from the pilot study is used. Also it is assumed that the Control group response will be half of that of the Active group and equal variability in both groups with common standard deviation of 13.2, a 50% coefficient of variation in the Active group.

Based on the above assumptions, a sample size of 17 subjects in each group will have 80% power to detect a difference between the Treatment PoNS™ group mean μ_A , of 26.3 and the Control group mean μ_C , of 13.2 assuming that the common standard deviation is 13.2 using a two group t-test with a 0.05 two-sided significance level.

Previous experience in two controlled pilot studies, a drop-out rate of not more than 25% is estimated. Therefore, using conservative approach, the sample size for this study is increased from 34 to 44 subjects with 22 subjects in each arm.

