5.2 Final Analysis

The study statistician will perform the final analysis using the primary efficacy endpoints when all 44 subjects have completed their Week 26 visit. Just like at interim analysis, mean and SD of each group will be calculated. Student's *t*-test will be used to compare the two groups and *p*-value will be reported.

Secondary analyses will consider group differences on measurements at a visit as well as change from baseline.

Descriptive statistics will be calculated for outcome and demographic variables. Mean and SD will be used for numeric variables and count (percent) will be used for categorical variables. The percentage of subjects compliant in each group will be calculated. Statistical comparisons between the groups will be made using Student's t-test for numeric data and chi-squared procedures for categorical data.

Data for comparison between the treatments are collected at baseline, week 2, week 5, week 8, week 11, week 14, week 17, week 20, week 23, and week 26 visits. Each subject has up to 10 data points collected for each of the outcome variables. Data at the end of each Stage (week 2, week 14, week 26) will be used for statistical comparison between the treatment groups. Statistical comparison between groups will be based on Student's t-test.

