6.0 ANALYSIS POPULATION

6.1 Efficacy Population

Intent-to-Treat (ITT) Population: The ITT population consists of all subjects, who met the inclusion/exclusion criteria and were randomized to receive one of the two devices. Efficacy analysis based on ITT population dataset will be the primary analysis.

Per-Protocol (PP) Population: The PP population includes all subjects, who met the inclusion/exclusion criteria and were randomized to receive one of the two devices and who had no significant violations, such as not receiving the assigned device. Efficacy based on the PP population dataset will be the secondary analysis.

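### The Week 14 SOT comparison drops randomised subjects without a Week 14 score; this is not reconciled with the ITT population, the all-data statement or the Protocol's repeated-measures ANOVA

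*Protocol*

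**What the plan says.** **Missing data.** The Protocol (Missing Data) plans no replacement of dropouts and no imputation, citing the pilot nature of the study. It continues: "Instead we will do a complete case analysis as well as a sensitivity analysis to examine the effect of the missing outcome data". It does not define a complete case (per visit, or all 10 visits) and does not describe the sensitivity analysis. The SAP has no missing-data rule and no sensitivity analysis.

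**Population.** The Protocol (Data Analysis, under the interim bullet) states: "The primary analysis will be conducted under the intention-to-treat principal, and all data will be included". The next sentence again excludes imputation. SAP 6.1 defines ITT as all eligible randomised subjects and adds: "Efficacy analysis based on ITT population dataset will be the primary analysis".

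**Method.** SAP 4.3 makes the changes from baseline to Week 2 and to Week 14 the primary endpoints. SAP 5.2 compares the arms at the end of each stage: "Statistical comparison between groups will be based on" Student's t-test. The Protocol's Final Analysis bullet names a repeated-measures ANOVA over the 10 data points instead.

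**Timing and attrition.** SAP 3.1 allows for dropout of at most 25%. SAP 5.2 schedules the final analysis for when all 44 subjects have completed Week 26.

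**The concern.** A two-group t-test on Week 14 change can use only subjects who have a Week 14 SOT. A randomised subject who leaves at Week 8 has SOT scores on file, but they contribute nothing to that comparison. No section says how such a subject enters an analysis of the all-randomised population.

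The Protocol's ANOVA does not settle the matter. If it is run listwise over 10 visits, one missed visit up to Week 26 removes the subject, so it could lose more people than the t-test.

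Informative loss is plausible. The Protocol (Withdrawal from Study Participation) describes the intervention as rigorous and expects some participants to find it harder than they thought. Both documents assume that Control responds half as well as Active. If a weak early response prompts people to leave, Control would then lose more of them. The study exists partly to supply effect sizes for later trials, so a distorted Week 14 difference would carry into their sample sizes.

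**Working it through.** **Inputs from the documents (SAP 3.1).** "Alpha Level= 0.05"; "Two-sided Test"; power 80%. For Active, "the mean change of 26.3 in composite SOT score at the end of Week 2 visit from baseline from the pilot study is used". The Control mean is 13.2 and the common SD 13.2, so the difference is 26.3 − 13.2 = 13.1. Enrolment is 22 per arm and dropout at most 25%.

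**Assumptions not in the documents.** Week 2 and Week 14 changes are bivariate normal with correlation ρ of 0.5 to 0.7. Week 14 means equal the Week 2 means. Dropout is 25% overall, all between Weeks 2 and 14, and logistic in Week 2 change with slope 1.5 per SD.

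**Step 1: the plan's own figure.** The noncentral t has noncentrality 13.1 / (13.2 × √(2/n)) and 2n − 2 df.
- n = 17: 13.1 / 4.53 = 2.89, power 0.801.
- n = 16: 13.1 / 4.67 = 2.81, power 0.775.

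The stated 17 per arm is reproduced. With 25% loss, 22 × 0.75 = 16.5 per arm remain, so power under random dropout is about 0.78.

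**Step 2: bias formula.** If dropout depends only on Week 2 change, stayers in an arm have a mean Week 2 change that differs from the arm mean by some δ. Their mean Week 14 change then differs by ρδ. The bias in the complete-case difference is therefore ρ(δ_Active − δ_Control).

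**Step 3: one shared rule on absolute early change.** Centre the rule at (26.3 + 13.2)/2 = 19.75 and set its level for 25% dropout overall. Numerical integration gives:
- Active: 15% leave (22 × 0.85 = 18.7 remain), δ = 2.32.
- Control: 35% leave (22 × 0.65 = 14.3 remain), δ = 4.96.
- Bias = ρ × (2.32 − 4.96) = −2.64ρ, which is −1.3 at ρ = 0.5 and −1.8 at ρ = 0.7.

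If there is no true difference, the rule acts identically in both arms and the bias is zero.

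**Step 4: other mechanisms.** A rule centred on the arm's own mean, with 25% loss in that arm, gives δ = 3.66.
- Same arm-relative rule in both arms: ρ(3.66 − 3.66) = 0.
- Poor responders leave Control only, Active random: −3.66ρ = −1.8 to −2.6.
- Poor responders leave Active only, Control random: +1.8 to +2.6.
- Poor responders leave Active and good responders leave Control: +7.32ρ = +3.7 to +5.1.

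**Step 5: simulation of the complete-case t-test** (22 per arm, ρ = 0.5 to 0.7; ranges cover repeated runs).

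| Dropout mechanism | Bias, points | Power | Type I error |
|---|---|---|---|
| Random | about 0 | about 0.78 | about 5% |
| Same arm-relative rule | about 0 | 0.81–0.82 | about 5% |
| Shared absolute rule | −1.2 to −1.9 | 0.68–0.72 | about 5–6% |
| Poor responders leave Control only | −1.8 to −2.7 | 0.64–0.66 | 6.5–9.5% |
| Poor responders leave Active only | +1.9 to +2.6 | not meaningful (biased upward) | 6.5–8.6% |
| Opposite patterns by arm | +3.7 to +5.4 | not meaningful (biased upward) | 12–21% |

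At ρ = 0.3 the shared rule gives −0.8 points and power 0.73.

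**Step 6: using the early score.** An estimate that regresses Week 14 on Week 2 change within arm, and uses every randomised subject's Week 2 value, stayed within about 0.2 points of the truth in every scenario. Its spread was slightly larger under the shared rule (SD 4.8 against 4.5 at ρ = 0.5; 4.6 against 4.4 at ρ = 0.7). Expected estimate over SD is 13.1/4.8 = 2.7 against 11.9/4.5 = 2.6 at ρ = 0.5, and 13.1/4.6 = 2.8 against 11.2/4.4 = 2.5 at ρ = 0.7. In this two-visit check the gain is mainly removal of bias, with some power at the higher correlation.

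**The case against.** **The plan does not flatly contradict ITT.** A reader might infer that it does. But the Protocol's Compliance section explains ITT as not removing subjects for non-compliance, and the all-data sentence is followed at once by the exclusion of imputation. All data can therefore mean all observed data. It also sits under the interim bullet. This objection stands: the documents support unreconciled, not contradictory.

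**The complete-case t-test is not stated as such anywhere.** It joins the Protocol's missing-data rule to the SAP's test. That is correct, and the conflict over the final method is part of the point.

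**Mitigation exists.** A sensitivity analysis is promised, and both Protocol sections commit to seeking follow-up on subjects who withdraw from treatment, which would reduce missingness. However, the sensitivity analysis is unspecified and absent from the SAP.

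**Week 2 is its own endpoint.** If cases are per visit, someone who leaves after Week 2 still counts there. Scores at Weeks 5, 8 and 11 are left out of the SAP's between-group tests for completers too, so that is a design choice and not an effect of dropout.

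**The inputs lean toward the unfavourable side.** The 25% is a ceiling with no stated timing, and some losses may follow Week 14. The correlation and slope are assumed. The near-zero bias in Step 6 follows from simulating dropout that depends only on observed Week 2 change.

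**Conclusion.** The point holds in a limited form. As written, randomised subjects without a Week 14 score leave the Week 14 comparison, and the documents do not reconcile this with the ITT population or agree on the final method.

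The most relevant scenario is the shared rule on absolute early response, because it needs no arm-specific behaviour in a double-blind trial and uses the plan's own assumption about Control. It gives a difference about 1 to 2 points too small, against 13.1 planned and the 8 points that the Protocol treats as clinically significant. Power is about 68–72% instead of about 78%, and type I error stays near nominal. These figures rest on the assumed correlation, slope, and amount and timing of dropout.

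Two stronger inferences are not supported. The first is that the analysis is biased whenever early response drives dropout: with the same arm-relative rule in both arms, the bias is about zero. The second is that the false-positive rate is 12–21%: that needs opposite mechanisms in the two arms, which nothing in the documents suggests.

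**What to change.** - In SAP 5.2 and the Protocol's Final Analysis bullet, name one primary method: a likelihood-based repeated-measures model of all observed post-baseline SOT scores through Week 14 (Weeks 2, 5, 8, 11 and 14) in all randomised subjects.
- Include baseline SOT, arm, visit, arm-by-visit and a small-sample degrees-of-freedom correction. Report the Week 2 and Week 14 contrasts. The choice of covariance structure should be stated in advance.
- Define complete case, and keep the complete-case t-test as a pre-specified sensitivity analysis in the SAP.
- Time the final analysis for when all subjects have completed or left the study, since 44 completers cannot be expected with dropout and no replacement.

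The model needs no imputation, so it fits the sponsor's stated choice, and the SOT scores are already scheduled. The cost is SAP and Protocol wording and modest programming in SAS or R. The model assumes missing at random, which is weaker than the assumption behind the complete-case t-test but would still fail if dropout depended on unobserved scores.

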- University of Wisconsin – Madison Health Sciences Human Subjects IRB.
- University of Wisconsin – Institute for Clinical and Translational Research – Data Monitoring Committee.

Coded data (results only) will be shared with the MRMC via secure email for purposes of informing future studies.

Statistical Considerations

Sample Size Estimation

This study will be an experimental investigation and will employ descriptive statistics to discover the mean changes from baseline for Control and Active, and then calculate true effect sizes and corresponding variances both within and between the two treatment groups. It is a first step in an iterative, incremental process to generate enough data to make reasonable power calculations in subsequent controlled studies. We believe this approach is justified because we have a very small data set from which to draw estimates of effect size, and none regarding a control group response. Our estimates are based on large changes in SOT scores in the previous pilot study involving 4 civilian subjects with mild to moderate concussive TBI using an Active device.

For this study we have assumed that the Control group response will be half that of the active group. Using a two-sample *t*-test to estimate the sample sizes of the experimental group and the control group, and assuming equal variances in the two treatment groups with $\sigma = 0.5$; a 2-tailed significance level, $\alpha = 0.05$; the true difference of the means = 0.5, and setting the power at 0.80, we calculate that a cohort of 17 subjects in each arm is sufficient. Based on our previous experience in two controlled pilot studies, we estimate a drop-out rate of not more than 25%. In using this conservative estimate, we believe the study is sufficiently powered at 22 subjects per treatment group (44 subjects total) to generate the data necessary to calculate effect sizes and cohorts in the future.

Primary Endpoints and Observational Measures

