Also, the statistician will present these results to the sponsor of the study but in the blinded fashion by identifying the treatment groups only as Group 1 and Group 2.

- **Final Analysis:** A repeated-measures ANOVA will be performed on the data derived from the 10 outcome measures gathered for each subject. Both individual (*n*=1) and cohort data set (*n*=22) analysis will be conducted to identify both specific and generalizable effects of the intervention methods. Sub-analysis by gender and age in both treatment groups will also be performed to assess the relative response of females and males.

Evidence of efficacy will be determined by significant differences in outcome measures both within and between groups after both the two-week intensive phase and at conclusion of the 14 weeks. Changes of 8 points in the SOT are considered clinically significant.

Data logs for each individual will be entered into the OnCore Data Management System used by ICTR for independent analysis and experimental verification.

Risks/Benefits Assessment

Potential Risks

1. **Electrotactile Stimulation.** The sensation could become uncomfortable at high intensity levels, which could be distressing to the subject. Some subjects have reported a mild tingling sensation that lasts from several minutes up to an hour after the stimulus is turned off. Although this sensation may feel unusual, it is not reported to be annoying and does not interfere with normal activities.

2. Excess Salivation. Subjects may experience excess salivation due to the presence of the PoNS in the mouth.
3. Disease Transmission. Because more than one subject may use the same device, there is a potential for disease transmission.
4. Falls. Subjects will be performing balance and gait tasks that may cause them to lose their balance or fall.
5. Decreased Performance or No Improvement in Symptoms. There is a risk that when subjects stop using the device, they will not retain any improvements they may have gained while doing CN-NINM training and their function will return to its prior level. There is also the possibility that CN-NINM training will not improve their symptoms.
6. Confidentiality. There is a risk that someone who is not involved in performing or monitoring this study could view study information.

Minimizing Risk

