Task fMRI: 1) In order to evaluate regions involved in balance processing, a checkerboard pattern will be used as the basis for a 2-dimensional visual stimuli in an optic flow task. A static checkerboard of alternating black and white squares will be used (CBstat) as the control stimulus. A rotating checkerboard (CBrot) will also be employed, in which the image appears to cyclically approach and recede relative to the observers' viewpoint, as well as rotate about the center of the viewfield [22]. During the scan, subjects will be shown the visual stimuli using a pseudo-randomized block-design paradigm. Each stimulus will be displayed for twelve seconds in blocks of three to six repetitions. Within a block, the stimulus presentations will be separated by six seconds of fixation to reduce the contamination of neural responses from one stimulus presentation into the next [23]. Each block will be separated by six seconds of fixation. The order of stimulus presentation will be the same for all subjects. Task scan will be approximately 7-8 minutes. **2)** In order to evaluate CNV, subjects will perform a jaw-clenching task, in which subjects will alternate between 20 seconds of jaw-clenching and 20 seconds of rest for a total of 6 cycles or 4 minutes. **3)** In order to evaluate CNV, VII, CNXII, subjects will perform a tongue thrust task in which they will alternate between thrusting their tongue to the roof of the mouth for 20 seconds and 20 seconds of rest for a total of 6 cycles or 4 minutes. We will also evaluate relationship of these brain MRI measures with balance and gait measures for the two treatment groups at each of the four time-points.

Each fMRI sub-study scan will take approximately 60 minutes to complete. All MRI scans will be performed at the Wisconsin Institutes for Medical Research (WIMR), [name].

Statistical Analysis

Task MRI Outcomes: Percent signal change will be computed for specific ROIs based on our previous work [11]. A repeated measures ANOVA will be used with Time (pre-intervention, stage 1, 2 3) as factor to examine change in percent signal over time in the patient group. To assess specific changes due to our intervention, we will perform paired t-tests (pre-intervention & stage 1; pre-intervention & stage 2 etc.). 2-sample t-tests will be used to compare differences between the Active PoNS group and control group.

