4.3 Primary Efficacy Endpoints

The primary efficacy endpoint is the change in the SOT score from Baseline to the Week 2 and Week 14 visits. That is, if X_1 is the endpoint then:

$$X_1 = \text{Composite SOT score at Week 2 visit} - \text{Composite SOT score at Baseline.}$$

Similarly, X_2 is:

$$X_2 = \text{Composite SOT score at Week 14 visit} - \text{Composite SOT score at Baseline.}$$

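### The protocol's final analysis, a repeated-measures ANOVA over all 10 visits with no sphericity handling, can exceed its 5% error rate and does not test the stated Week 2 and Week 14 efficacy criterion

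*Protocol*

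**What the plan says.** Protocol, Data Analysis, Final Analysis: "A repeated-measures ANOVA will be performed on the data derived from the 10 outcome measures gathered for each subject". The number 10 refers to visits. The Study Design section gives 10 data points per subject on the SOT and gait metrics, whereas one primary and 11 observational measures would make 12 variables. The sentence does not say which F test counts (group, time or group-by-time), what covariance is assumed, or whether a correction is applied.

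The next paragraph of that section rests evidence of efficacy on "significant differences in outcome measures both within and between groups after both the two-week intensive phase and at conclusion of the 14 weeks".

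SAP 4.3: "The primary efficacy endpoint is the change in the SOT score from Baseline to the Week 2 and Week 14 visits". SAP 5.2: "Student's *t*-test will be used to compare the two groups and *p*-value will be reported", and later "Data at the end of each Stage (week 2, week 14, week 26) will be used for statistical comparison between the treatment groups". The SAP contains no repeated-measures ANOVA.

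Protocol, Sample Size Estimation: after naming a two-sample t-test, "we calculate that a cohort of 17 subjects in each arm is sufficient".

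MRI sub-study addendum, Statistical Analysis, for task fMRI: "A repeated measures ANOVA will be used with Time (pre-intervention, stage 1, 2 3) as factor". The DTI outcomes use the same form. Active and Control are compared there by two-sample t-tests.

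**The concern.** The usual within-subject F test holds its nominal level only if all differences between pairs of visits have the same variance (sphericity). Here the visits span 26 weeks and three stages: in-lab training, home training, and stopping the device. Visits three weeks apart are likely to be more alike than visits six months apart, and that breaks the condition. An uncorrected group-by-time F then rejects too often when the arms do not differ.

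The second problem is the target of the test. A 10-visit F asks whether the arms' profiles differ anywhere over 26 weeks. The protocol's own criterion concerns two visits. Four of the 10 visits come after the device is stopped, and a difference that arises only there would make the named final analysis significant without showing anything about the effect of training with the device.

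Because the term and the correction are left open, they could also be chosen after the data are seen.

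**Working it through.** **1. The plan's own figure.** The protocol assumes difference 0.5 and SD 0.5, so d = 1.0. The SAP assumes 26.3 − 13.2 = 13.1 and SD 13.2, so d = 0.99. The normal approximation n = 2(1.96 + 0.84)²/d² gives 15.7, or 16 per arm, at d = 1.0. Exact noncentral-t power at 17 per arm is 80.7% (protocol) and 80.1% (SAP). The 17 per arm is therefore reproduced, for a two-sample t-test on change at one visit.

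**2. What the 10-visit F tests.** Visits: 1 baseline + 5 in training (Weeks 2, 5, 8, 11, 14) + 4 in withdrawal (Weeks 17, 20, 23, 26) = 10. The group-by-time term has (2 − 1)(10 − 1) = 9 numerator degrees of freedom. At 22 per arm the denominator has (44 − 2) × 9 = 378. The stated criterion uses 2 contrasts: Week 2 minus baseline and Week 14 minus baseline.

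**3. Error rate of the uncorrected group-by-time F.** The departure from sphericity is measured by ε = [tr(CΣC)]² / {9 · tr[(CΣC)²]}, where Σ is the covariance over the 10 visits and C is the centring matrix. ε = 1 means sphericity holds, and Greenhouse-Geisser multiplies both degrees of freedom by an estimate of ε. The documents give no correlations, so the structures below are assumptions. The rates come from simulation with no group difference, 22 per arm, 10,000 trials per case, nominal 5%. The standard error is about √(0.05 × 0.95/10,000) = 0.2 points near 5%.

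| Correlation per visit step | ε | 9ε | Uncorrected F | Greenhouse-Geisser |
|---|---|---|---|---|
| 0.7 | 0.499 | 4.5 | 9.9% | 4.8% |
| 0.8 | 0.411 | 3.7 | 10.4% | 4.5% |
| 0.9 | 0.333 | 3.0 | 11.4% | 5.0% |
| 0.95 | 0.298 | 2.7 | 12.1% | 4.7% |

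Weaker decay gives 5.8% (0.3 per step) and 7.2% (0.5 per step). A random intercept plus decay gives about 7–11%, a random slope about 6%, and constant correlation 5%. The corrected F is about 4–5%, and 3% in the most conservative case.

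A check without simulation at 0.7 per step: the uncorrected critical value of F(9, 378) is 1.905. Under Box's approximation the statistic follows F(9 × 0.499, 378 × 0.499) = F(4.5, 188.6), which exceeds 1.905 with probability 10.3%, against 9.9% simulated. At 0.9 per step the approximation gives 13.2% against 11.4% simulated, so it overstates somewhat; the simulated figures are used here.

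In the same simulations the group main effect and the t-tests on change at Week 2 and Week 14 stayed near 5%, each taken as a single comparison.

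**4. A difference that arises only after the device is stopped.** Let the arms be equal through Week 14 and drift apart evenly to 8 points at Week 26 (8/4 = 2 points per withdrawal visit). With the SD of the Week 14 change set to 13.2 and 17 per arm, the uncorrected 10-visit group-by-time F is significant in about 41–47% of trials across the structures tried. In this scenario the true between-arm difference at Week 2 and at Week 14 is zero. A sphericity correction lowers the figure but does not change the hypothesis being tested.

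**The case against.** The strongest reply is that the ANOVA may not be the efficacy test at all. The protocol ties efficacy to two time points and the SAP tests those changes by t-test at 5% per comparison. If the SAP governs, neither problem reaches the main between-group result. A withdrawal-only divergence also would not meet the protocol's written criterion. This limits the consequence, but the ANOVA remains in the current protocol as the named final analysis.

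It is also fair that the protocol never says the F will be uncorrected. That is an inference from silence, and under constant correlation the rate is 5%. The study is described as a pilot-scale, largely descriptive investigation.

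A reader might go further and infer that the ANOVA lacks the stated 80% power because half its visits carry no on-device effect. The documents do not support this, for four reasons:

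- The sample-size text already names the two-sample t-test and claims nothing for an ANOVA.
- Four visits, not five, are in withdrawal; the count reaches half only by including baseline. The size of any effect after withdrawal is not stated.
- No-effect withdrawal visits raise the power of the group-by-time F. At 17 per arm with 13.1 points and the SD of the Week 14 change at 13.2, the corrected F has 98–100% power if the effect vanishes after Week 14 and about 54–72% if it is fully retained. If 13.2 is instead the SD of the Week 2 change, the levels fall as correlation decays, but the direction is the same: uncorrected 59% against 27% at 0.9 per step.
- Dilution affects only the group main effect, whose error rate stays near 5%. No single F has both faults.

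Nor do the between-arm figures carry over to the MRI addendum, where Time is the only ANOVA factor and arms are compared by t-tests.

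**Conclusion.** The point stands in two parts. First, the named ANOVA leaves term, covariance and correction open, and the uncorrected group-by-time version would run at about 6–12% instead of 5% if correlation fades over the 26 weeks. The range depends wholly on assumed correlations. Constant correlation, which would give 5%, is the least plausible case in a train-then-stop design. Second, whatever its error rate, a 10-visit F does not answer the protocol's Week 2 and Week 14 question. The 41–47% figure shows how far withdrawal visits alone can drive it; it assumes an 8-point drift and an SD of 13.2 for the Week 14 change, and would be smaller with a larger SD.

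The finding does not extend to the group main effect or to the SAP t-tests. It is not a finding that the trial is underpowered, and Sample Size Estimation needs no change on this account. For the MRI addendum only the sphericity point applies, to the within-subject Time F. The plan should be changed, because the better method is already in the SAP and costs almost nothing.

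**What to change.** In the protocol's Final Analysis paragraph:

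- Base between-group efficacy on the changes in composite SOT from baseline to Week 2 and to Week 14, in line with SAP 4.3 and 5.2. Take them either from the SAP t-tests or as contrasts from a mixed model with unstructured covariance, and say which is primary.
- If an ANOVA F is kept for efficacy, limit it to baseline through Week 14, name the term (group-by-time), and report it with Greenhouse-Geisser correction.
- Analyse Weeks 17 to 26 separately, as the withdrawal question.

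In the MRI addendum, apply the same correction to the within-subject Time F for the task fMRI and DTI outcomes.

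The cost is wording in the protocol and a matching line in the SAP; the correction is standard software output. Any F that is kept will have slightly larger p-values, and withdrawal visits no longer count towards the efficacy test. If the mixed model is chosen, fitting it to baseline through Week 14 needs 6 × 7/2 = 21 covariance parameters, against 10 × 11/2 = 55 for all visits, which is more realistic with 44 subjects.
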